12.4.4.2 Chest X-ray

Chest CT scan is preferred over chest X-ray, particularly when recurrence is an important endpoint, because CT is more sensitive than X-ray, particularly in identifying new lesions. However, lesions on chest X-ray may be considered measurable if they are clearly defined and surrounded by aerated lung.

12.4.4.3 CT and MRI scans

CT is the best currently available and reproducible method to measure lesions selected for response assessment. In this guideline, the definition of measurability of lesions on CT scan is based on the assumption that CT slice thickness is ≤ 5 mm. When CT scans have slice thickness of > 5 mm, the minimum size for a measurable lesion should be twice the slice thickness. MRI is also acceptable. If prior to enrollment it is known that a patient is unable to undergo CT scans with IV contrast

Columbia University Irving Medical Center
Herbert Irving Comprehensive Cancer Center
AAAS4165_Version Date: 07/07/2021

because of allergy or renal insufficiency, the decision as to whether a non-contrast CT scan or MRI (without IV contrast) will be used to evaluate the patient at baseline and during the study should be guided by the tumor type under investigation and the anatomic location of the disease. For patients who develop contraindications to contrast after baseline contrast CT scan is done, the decision as to whether non-contrast CT scan or MRI (enhanced or non-enhanced) will be performed should also be based on the tumor type and the anatomic location of the disease, and should be optimized to allow for comparison with the prior studies if possible. Each case should be discussed with the site- designated radiologist to determine if substitution of these other approaches is possible. If not, the patient should be considered not evaluable from that point forward. Care must be taken in measuring target lesions and interpreting non-target disease or new lesions on a different modality, because the same lesion may appear to have a different size using a new modality.

12.4.4.4 FDG-PET

While FDG-PET response assessments need additional study, it is sometimes reasonable to incorporate the use of FDG-PET scanning to complement CT scanning in assessment of recurrence (particularly possible 'new' disease). New lesions on the basis of FDG-PET imaging can be identified according to the following algorithm:

- Negative FDG-PET at baseline, with a positive FDG-PET at follow-up is a sign of progressive disease (PD) based on a new lesion.
- No FDG-PET at baseline and a positive FDG-PET at follow-up: If the positive FDG-PET at follow-up corresponds to a new site of disease confirmed by CT scan, this is PD, which should be confirmed by a biopsy. If the positive FDG-PET at follow-up is not confirmed as a new site of disease on CT, additional follow-up CT scans are needed to determine if there is truly progression occurring at that site (if so, the date of PD will be the date of the initial abnormal FDG-PET scan). If the positive FDG-PET at follow-up corresponds to a pre-existing site of disease on CT that is not progressing on the basis of the anatomic images, this is not PD.
- FDG-PET may be used to upgrade a response to a complete response (CR) in a manner similar to a biopsy in cases where a residual radiographic abnormality is thought to represent fibrosis or scarring. The use of FDG-PET in this circumstance should be prospectively described in the protocol and supported by disease-specific medical literature for the indication. However, it must be acknowledged that both approaches may lead to false positive CR due to limitations of FDG-PET and biopsy resolution/sensitivity.

Note: A 'positive' FDG-PET scan lesion means one that is FDG avid with an uptake greater than twice that of the surrounding tissue on the attenuation corrected image.

Columbia University Irving Medical Center
Herbert Irving Comprehensive Cancer Center
AAAS4165_Version Date: 07/07/2021

12.4.4.5 Endoscopy, laparoscopy, ultrasound, tumor markers, cytology, histology

Endoscopy, laparoscopy, ultrasound, tumor markers, cytology, and histology cannot be utilized for objective tumor evaluation.

12.4.5 Assessment of tumor burden

To assess recurrence, it is necessary to estimate the overall tumor burden at baseline and use this as a comparator for subsequent measurements.

12.4.6 Definition of target and non-target lesions

Baseline scan should be that which is considered optimal for the particular histology.

Target lesions should be selected on the basis of their size (lesions with the longest diameter) and be representative of all involved organs, but in addition should lend themselves to reproducible repeated measurements. It may be the case that, on occasion, the largest lesion does not lend itself to reproducible measurement, in which case the next largest lesion that can be measured reproducibly should be selected.

Lymph nodes merit special mention because they are normal anatomical structures that may be visible by imaging, even if not involved by tumor. As noted above, pathological nodes that are defined as measurable and may be identified as target lesions must meet the criterion of a short axis of ≥ 15 mm by CT scan. Only the short axis of these nodes will contribute to the baseline sum. The short axis of the node is the diameter normally used by radiologists to judge if a node is involved by solid tumor. Lymph node size is normally reported as two dimensions in the plane in which the image is obtained (for CT, this is almost always the axial plane; for MRI, the plane of acquisition may be axial, sagittal, or coronal). The smaller of these measures is the short axis. For example, an abdominal node that is reported as being 20 mm \times 30 mm has a short axis of 20 mm and qualifies as a malignant, measurable node. In this example, 20 mm should be recorded as the node measurement. All other pathological nodes (those with short axis ≥ 10 mm but < 15 mm) should be considered non-target lesions. Nodes that have a short axis of < 10 mm are considered non-pathological and should not be recorded or followed.

All lesions (or sites of disease) not selected as target lesions (measurable or non-measurable), including pathological lymph nodes, should be identified as non-target lesions and should also be recorded at baseline. Measurements are not required. It is possible to record multiple non-target lesions involving the same organ as a single item on the CRF (e.g., "multiple enlarged pelvic lymph nodes" or "multiple liver metastases").

12.4.7 New lesions

New lesions identified after baseline will be evaluated for measurability with use of the same criteria applied to prospective target lesions at baseline per RECIST [e.g., non-lymph node lesions must be ≥ 10 mm on the longest diameter; new lymph nodes must be ≥ 15 mm on the short axis (see note below)]. All new lesions (measurable or non-measurable) must be assessed and recorded at the time of identification and at all subsequent tumor assessment time points.

Up to a maximum of five measurable new lesions total (and a maximum of two lesions per organ) can be included in the calculation of tumor burden that is performed as part of the tumor response evaluation. New lesion types that would not qualify as target lesions per RECIST cannot be included in the calculation of tumor burden and thus will not affect overall tumor response evaluation. New lesions that are not measurable at first appearance but meet measurability criteria at a subsequent time point can be included in the tumor response evaluation from that point on, if the maximum number of measurable new lesions has not been reached.

Note regarding new lymph node lesions: If at first appearance the short axis of a lymph node lesion is ≥ 15 mm, it will be considered a measurable new lesion. If at first appearance the short axis of a lymph node lesion is ≥ 10 mm and < 15 mm, the lymph node will not be considered measurable, but will still be considered a new lesion and should be identified as a non-measurable new lesion. If at first appearance the short axis of a lymph node is < 10 mm, the lymph node should not be considered pathological and should not be considered a new lesion. A lymph node can subsequently become measurable, when the short axis is ≥ 15 mm.

12.4.8 Calculation of sum of diameters

A sum of the diameters (longest diameter for non-lymph node lesions, short axis for lymph node lesions) will be calculated for all target lesions at baseline as a measure of tumor burden. At each subsequent tumor assessment, a sum of the diameters (longest diameter for non-lymph node lesions, short axis for lymph node lesions) will be calculated for all target lesions plus measurable new lesions (up to five new lesions, with a maximum of two new lesions per organ) that have emerged after baseline. Hence, each net percentage change in tumor burden per assessment accounts for the size and growth kinetics of both old lesions and new lesions as they appear.

12.4.8.1 Measuring Lymph Nodes

If at first appearance the short axis of a new lymph node lesion is ≥ 15 mm, it will be considered a measurable new lesion and may be included in the sum of the diameters. If the new lymph node lesion is included in the sum of diameters, it will continue to be measured and included in the sum of diameters at subsequent time points, even if the short axis decreases to < 15 mm (or even < 10 mm). However, if it subsequently decreases to < 10 mm and all other lesions are no longer detectable or have also decreased to a short axis of < 10 mm (if lymph nodes), a response assessment of complete response may be assigned.

Lymph nodes should always have the actual short axis measurement recorded (measured in the same anatomical plane as the baseline examination), even if the node regresses to < 10 mm during the study. Thus, when lymph nodes are included in the sum of diameters, the sum may not be zero even if complete response criteria are met, because a normal lymph node is defined as having a short axis of < 10 mm.

12.4.8.2 Measuring Lesions That Become Too Small to Measure

During the study, all target lesions and up to five measurable new lesions (lymph node and non-lymph node) should have their actual measurements recorded at each subsequent evaluation,

even when very small (e.g., 2 mm). However, sometimes lesions or lymph nodes become so faint on CT scan that the radiologist may not feel comfortable assigning an exact measurement and may report them as being too small to measure. When this occurs, it is important that a value be recorded on the CRF, as follows:

- If it is the opinion of the radiologist that the lesion has likely disappeared, the measurement should be recorded as 0 mm.
- If the lesion is believed to be present, but too small to measure, a default value of 5 mm should be assigned and "too small to measure" should be ticked. (Note: It is less likely that this rule will be used for lymph nodes because they usually have a definable size when normal and are frequently surrounded by fat, such as in the retroperitoneum; however, if a lymph node is believed to be present and is faintly seen but too small to measure, a default value of 5 mm should be assigned in this circumstance as well, and "too small to measure" should also be ticked).

To reiterate, however, if the radiologist is able to provide an actual measurement, that measurement should be recorded, even if it is < 5 mm, and in that case "too small to measure" should not be ticked.

12.4.8.3 Measuring lesions that split or coalesce on treatment

When non-lymph node lesions fragment, the longest diameters of the fragmented portions should be added together to calculate the sum of diameters. Similarly, as lesions coalesce, a plane between them may be maintained that would aid in obtaining maximal diameter measurements of each individual lesion. If the lesions have truly coalesced such that they are no longer separable, the vector of the longest diameter in this instance should be the maximum longest diameter for the coalesced lesion.

12.4.8.4 Evaluating non-target lesions and non-measurable new lesions

Measurements are not required for non-target lesions or non-measurable new lesions. Non-target lesions should be noted at baseline, and non-measurable new lesions should be noted at the time of identification. At subsequent evaluations, non-target lesions and non-measurable new lesions will be categorized as "present" or "absent."

After baseline, changes in non-target lesions or non-measurable new lesions (or measurable new lesions in excess of 5 total or 2 per organ) will contribute only in the assessment of complete response (i.e., a complete response is attained only with the complete disappearance of all tumor lesions, including non-target lesions and non-measurable new lesions) and will not be used to assess progressive disease.

12.5 Missing assessments and not-evaluable designation

When no imaging/measurement is done at all at a particular time point, the patient is not evaluable at that time point. If measurements are made on only a subset of target or measurable new lesions at a time point, usually the case is also considered not evaluable at that time point, unless a convincing argument can be made that the contribution of the individual missing lesions would not change the assigned time point response. This would be most likely to happen in the case of treatment beyond recurrence. For example, if a patient had a recurrence sum of 50 mm with three measured lesions, and during the study only 2 lesions were assessed, but those gave a sum of 80 mm, the patient will have achieved confirmed recurrence status, regardless of the contribution of the missing lesion.

12.6 Special notes on response assessment

Patients with a global deterioration in health status requiring discontinuation of treatment without objective evidence of disease recurrence at that time should be reported as having "symptomatic deterioration." Every effort should be made to document objective recurrence even after discontinuation of treatment. Symptomatic deterioration is not a descriptor of an objective response; it is a reason for stopping study therapy. The objective response status of such patients is to be determined by evaluation of target and non-target lesions, as well as new lesions.

12.7 Definitions

Evaluable for toxicity: All Participants will be evaluable for toxicity from the time of their first treatment with study drug.

Evaluable for objective response: Only those Participants who have measurable disease present at baseline, have received at least one cycle of therapy, and have had their disease re-evaluated will be considered evaluable for response. These Participants will have their response classified according to the definitions stated below. (Note: Participants who exhibit objective disease progression prior to the end of cycle 1 or who die prior to tumor assessment will also be considered non- responders).

Measurable disease: Measurable lesions are defined as those that can be accurately measured in at least one dimension (longest diameter to be recorded for non-nodal lesions and short axis for nodal lesions) as ≥ 20 mm by chest x-ray, as ≥ 10 mm with CT scan, or ≥ 10 mm with calipers by clinical exam. All tumor measurements must be recorded in millimeters (or decimal fractions of centimeters).

Note: *Tumor lesions that are situated in a previously irradiated area are not considered measurable.*

Malignant lymph nodes: To be considered pathologically enlarged and measurable, a lymph node must be ≥ 15 mm in short axis when assessed by CT scan (CT scan slice thickness recommended to be no greater than 5 mm). At baseline and in follow-up, only the short axis will be measured and followed.

Non-measurable disease: All other lesions (or sites of disease), including small lesions (longest diameter <10 mm or pathological lymph nodes with ≥ 10 to <15 mm short axis), are considered non-measurable disease. Bone lesions, leptomeningeal disease, ascites, pleural/pericardial effusions, lymphangitis cutis/pulmonitis, inflammatory breast disease, and abdominal masses (not followed by CT or MRI), are considered non-measurable.

Note: Cystic lesions that meet the criteria for radiographically-defined simple cysts should not be considered as malignant lesions (neither measurable nor non-measurable) since they are, by definition, simple cysts. Cystic lesions thought to represent cystic metastases can be considered as measurable lesions if they meet the definition of measurability described above. However, if non-cystic lesions are present in the same patient, these are preferred for selection as target lesions.

Target lesions: All measurable lesions up to a maximum of 2 lesions per organ and 5 lesions in total, representative of all involved organs, should be identified as target lesions and recorded and measured at baseline. Target lesions should be selected on the basis of their size (lesions with the longest diameter), be representative of all involved organs, and be those that lend themselves to reproducible repeated measurements. It may be the case that, on occasion, the largest lesion does not lend itself to reproducible measurement, in which circumstance the next largest lesion that can be measured reproducibly should be selected. A sum of the diameters (longest for non-nodal lesions, short axis for nodal lesions) for all target lesions will be calculated and reported as the baseline sum diameters. If lymph nodes are to be included in the sum, then only the short axis is added into the sum. The baseline sum diameters will be used as reference to further characterize any objective tumor regression in the measurable dimension of the disease.

Non-target lesions: All other lesions (or sites of disease), including any measurable lesions over and above the 5 target lesions should be identified as non-target lesions and should also be recorded at baseline. Measurements of these lesions are not required, but the presence, absence, or in rare cases unequivocal progression of each should be noted throughout follow-up.

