3.1.4.2 Effect of atezolizumab in combination with cobimetinib

The randomized phase 3 IMblaze370 study tested combination atezolizumab and cobimetinib versus atezolizumab or regorafenib alone in patients with advanced colorectal cancer who had progressed on or were intolerant of two lines of therapy. Of those treated with atezolizumab and cobimetinib, 61% experienced Grade 3/4 adverse events compared to 58% who were treated with regorafenib, an approved drug for metastatic colorectal adenocarcinoma. Diarrhea (11%), anemia (6%), increased blood creatine phosphokinase (7%), and fatigue (4%) were the most commonly observed all-cause Grade 3 – 4 toxicities in subjects treated with cobimetinib and atezolizumab (SAEs were reported in 40% subjects receiving combination therapy). Of the AEs, 26% of subjects experienced serious treatment-related AEs, 21% stopped treatment, and 61% required dose interruption or modification (Eng et al., 2019).

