Statistical analysis of RNA-Seq expression data derived from samples of the treatment arms will be carried out in the R environment for statistical computing (RDC, 2016). In order to identify differentially expressed genes between the conditions, we will make use voom-limma framework (Ritchie et al., 2015). Briefly, linear models are fit for each gene to estimate the coefficients (= effect size) and their standard error. Empirical Bayes-moderated t-statistics and their associated p-values are then used to assess the significance of the observed expression changes.

In order to evaluate concerted differences of biologically related genes, single sample gene set enrichment will be employed via the GSVA R package (Hanzelmann, Castelo, & Guinney, 2013) which produces a gene-set by sample matrix with approximately normally distributed enrichment scores which can then be compared between treatment arms using for example linear models. Detailed statistical plan is as described in the manuscript [[name], submitted].

Columbia University Irving Medical Center
Herbert Irving Comprehensive Cancer Center
AAAS4165_Version Date: 07/07/2021

4.1.2 Phase 2

The phase 2 portion of the study will be amended after preliminary safety and efficacy results from phase 1 and other ongoing clinical trials have been analyzed and a summary incorporated within the protocol as an amendment including a rationale of the cohorts to be tested. The amendment will be submitted to the Scientific Review Committee (PRMC) and Institutional Review Board (IRB) at CUIMC for approval prior to activation of phase 2 portion of the study.

Three separate phase 2 studies will be conducted based on the differences in baseline response rate by disease subtype:

Cohort 1 – Advanced Pancreas Adenocarcinoma

Cohort 2 – Advanced Colorectal Adenocarcinoma

Cohort 3 – Histology Agnostic Adenocarcinoma

The primary outcome measure is best objective response by 16 weeks; that is, patients who achieve CR or PR within the first 16 weeks will be considered responders. Tumor response will be assessed by CT scans performed every 8 weeks using the Immune-Modified Response Evaluation Criteria in Solid Tumors (IM RECIST). We will use a Simon optimal 2-stage design for each disease subtype to allow for early stopping.

Advanced Pancreas Adenocarcinoma

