For the advanced pancreas adenocarcinoma group, we assume an objective response rate of 16%, based on current therapy (Wang-Gillam et al., 2016). The study will enroll 23 patients in the first stage. If 5 or more patients respond in the first stage, the study will be expanded to a total of 67 patients. If a total of 16 or more patients respond, the combination will be considered promising in patients with advanced pancreatic adenocarcinoma. This optimal two-stage design assumes for a type 1 error of 0.05 and type 2 error of 0.20 to detect a difference of 16%, versus 30% in the best objective response rate by 16 weeks.

Metastatic Colorectal Adenocarcinoma

For the advanced colorectal adenocarcinoma group, we assume an objective response rate of 2%, based on current therapy (Grothey et al., 2013; Mayer et al., 2015). The study will enroll 20 patients in the first stage. If 2 or more patients respond in the first stage, the study will be expanded to a total of 34 patients. If a total of 3 or more patients respond, the combination will be considered promising in patients with advanced colorectal adenocarcinoma. This optimal two-stage design assumes for a type 1 error of 0.05 and type 2 error of 0.20 to detect a difference of 2%, versus 15% in the best objective response rate by 16 weeks.

Advanced Histology Agnostic Adenocarcinoma

For the histology agnostic adenocarcinoma group, we assume an objective response rate of 5%, based on current therapy, and given the inclusion criteria that subjects must have progressed on or are intolerant of all standard of care therapies that result in a median progression free survival benefit of ≥ 8 weeks or an overall response rate of $> 5\%$. The study will enroll 23 patients in the first stage. If 2 or more patients respond in the first stage, the study will be expanded to a total of

Columbia University Irving Medical Center
Herbert Irving Comprehensive Cancer Center
AAAS4165_Version Date: 07/07/2021

56 patients. If a total of 6 or more patients respond, the combination will be considered promising in patients with histology agnostic adenocarcinoma. This optimal two-stage design assumes for a type 1 error of 0.05 and type 2 error of 0.20 to detect a difference of 5% versus 15% in the best objective response rate by 16 weeks.

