4.1.2.1 Size/Accrual Rate

The planned accrual size is 157 evaluable patients across the three cohorts of patients. The expected accrual rate is 4 patients per month. However, given the possibility of early stopping, the sample size could be as low as 66 if all three cohorts stop in the first stage.

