4.1.2.2 Analysis of Primary Endpoints

The frequency of best objective response (CR+PR) by 16 weeks will be calculated along with an exact 95% confidence interval.

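### The response-evaluable rule drops patients who stop early from the phase 2 denominator, so the response rate is biased upward; if they are replaced, type I error passes 0.05 in two of three cohorts

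*Combined protocol and SAP*

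**What the plan says.** Section 12.7 (Definitions) admits to the response analysis only participants who have measurable disease at baseline and who "have received at least one cycle of therapy, and have had their disease re-evaluated will be considered evaluable for response". The conditions are joined by 'and', so all must be met. A note to the definition brings back two groups as non-responders: "Participants who exhibit objective disease progression prior to the end of cycle 1 or who die prior to tumor assessment". No other early departure is brought back.

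Section 4.1.2.1 uses the same word for the phase 2 size: "The planned accrual size is 157 evaluable patients across the three cohorts of patients". The 157 is the sum of the three maximum Simon sizes, 67 + 34 + 56.

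Section 4.1.2 defines the endpoint: "patients who achieve CR or PR within the first 16 weeks will be considered responders". Section 4.1.2.2 gives the analysis, "The frequency of best objective response (CR+PR) by 16 weeks will be calculated along with an exact 95% confidence interval", and names no denominator. Section 4.1.2 describes each first stage as patients the study will enroll and states no replacement rule for phase 2. The replacement rules in section 4.1.1 concern evaluability for dose-limiting toxicity in phase 1.

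Three other places bear on who is lost:
- Section 5.5.1 takes patients off treatment for toxicity, non-compliance or withdrawn consent.
- Note 15 to Table 10 asks for end-of-study imaging when a patient leaves for a reason other than confirmed progression or death.
- Section 12.6 says symptomatic deterioration is not a response category, and that objective status is to be determined from the lesions.

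**The concern.** The primary endpoint drives a go/no-go decision in each single-arm cohort, so the denominator matters as much as the numerator. A patient who stops within the first cycle without objective progression or death is excluded by section 12.7 even if the exit scan is done, because the one-cycle condition fails. A patient who is never re-scanned fails the other condition. Neither can be counted as a responder under the rule, so exclusion depends on outcome. The direction is also awkward: the worse the regimen is tolerated early on, the more non-responders leave the denominator and the better the response rate looks.

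If the cohorts are then filled up to the evaluable number, the Simon boundaries are applied to a selected group, and an inactive regimen has a larger chance of being called promising than the stated 0.05.

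**Working it through.** **Inputs from section 4.1.2.** The stated limits are type I error 0.05 and type II error 0.20 in each cohort.

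| Cohort | p0 | p1 | Continue if | Promising if |
|---|---|---|---|---|
| Pancreas | 0.16 | 0.30 | ≥5 of 23 | ≥16 of 67 |
| Colorectal | 0.02 | 0.15 | ≥2 of 20 | ≥3 of 34 |
| Histology agnostic | 0.05 | 0.15 | ≥2 of 23 | ≥6 of 56 |

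**Formula.** With n1 first-stage patients, n in total, continuation boundary a1 and final boundary a, the probability of calling the regimen promising at response rate p is

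R(p) = Σ over x ≥ a1 of P[Bin(n1, p) = x] × P[Bin(n − n1, p) ≥ a − x].

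**Step 1: reproduce the plan.** R(p0) is 0.047, 0.020 and 0.050 (pancreas, colorectal, agnostic). R(p1) is 0.805, 0.801 and 0.800. All three designs meet the stated limits. Pancreas and agnostic have almost no room below 0.05; colorectal has a good deal.

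**Step 2: bias in the reported rate.** Let f be the share of treated patients who are excluded, and assume that none of them is a responder. If the all-treated rate is p, the rate among evaluable patients is p/(1 − f). At f = 10% a true 16% reads as 0.16/0.90 = 17.8%, 5% reads as 5.6%, and 2% reads as 2.2%.

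**Step 3: type I error with replacement.** Assume in addition that excluded patients are replaced until the evaluable n is reached, and that p0 is an all-treated rate. Type I error is then R(p0/(1 − f)) with the boundaries unchanged:

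| f | Pancreas | Histology agnostic | Colorectal |
|---|---|---|---|
| 0 | 0.047 | 0.050 | 0.020 |
| 1% | 0.051 | 0.052 | 0.021 |
| 2% | 0.055 | 0.054 | 0.021 |
| 5% | 0.069 | 0.061 | 0.023 |
| 10% | 0.100 | 0.075 | 0.026 |
| 15% | 0.144 | 0.092 | 0.030 |
| 25% | 0.285 | 0.142 | 0.042 |

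**Step 4: type I error without replacement.** The boundaries are counts of responders. If 67 pancreas patients are treated and the excluded ones are not replaced, they add nothing to the count and the rule still operates on 67 patients at p0. Type I error stays at 0.047, 0.020 and 0.050, and only the reported percentage and its interval are biased.

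**Step 5: effect of the remedy.** With all treated patients in the denominator and undocumented response counted as non-response, type I error is R(p0) again. Power stays at 0.805, 0.801 and 0.800 if p1 is an all-treated rate. If p1 was meant for evaluable patients, the all-treated alternative is p1(1 − f), and at f = 10% power is 0.66, 0.74 and 0.72 (pancreas, colorectal, agnostic).

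**The case against.** Several points on the other side have force.

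- **Replacement is inferred.** No phase 2 replacement rule is written, and section 4.1.2 speaks of enrolling the stage counts. Without replacement the decision rule is unaffected (step 4). This stands as a condition on the type I figures. It does not remove the bias in the reported rate, and the evaluable sizing in section 4.1.2.1 points towards replacement.
- **The link to section 12.7 is inferred.** The phase 2 analysis text does not cite that definition. But it is the only definition of evaluability for response in the document, and no all-treated response set is given.
- **The basis of p0 is not stated.** For pancreas the plan says only "we assume an objective response rate of 16%, based on current therapy". If p0 came from evaluable patients, the comparison in step 3 would not apply.
- **The exit scan and section 12.6 narrow the group.** A patient who stops for toxicity after a full cycle and has the required scan is evaluable, and early progression and death already count as non-response. What remains is first-cycle stops without either event, plus patients who miss the scan. That group is smaller than all early discontinuations, but it is not empty.
- **Phase 2 will be amended and reviewed before activation.** No patient is affected yet. That is a reason to settle the rule in the amendment.

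A reader might go further and take f from section 3.1.4.2, which reports for cobimetinib plus atezolizumab that "21% stopped treatment, and 61% required dose interruption or modification", and so read off a pancreas type I error above 0.2. The documents do not support that. The figure comes from another trial, is not limited to the time before a first re-scan, and includes patients whom the exit-scan rule would keep evaluable here. A reader might also infer that all three cohorts break their error limit; colorectal does not at any f up to 25%.

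**Conclusion.** The concern holds in a conditional form. As written, section 12.7 together with the evaluable sizing in section 4.1.2.1 removes treated patients who have no route to a counted response, and so biases the reported response rate upward by 1/(1 − f). This needs only that the excluded patients are non-responders.

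The effect on type I error rests on two further assumptions: that excluded patients are replaced to reach the evaluable n, and that p0 is an all-treated rate. Under both, the stated 0.05 is passed from about f = 1% in the pancreas and histology-agnostic cohorts. At f = 5% the values are 0.069 and 0.061. Colorectal rises but remains within its limit. Since the documents give no f, these figures are a sensitivity range and not a prediction.

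**What to change.** Change sections 12.7, 4.1.2.1 and 4.1.2.2 in the amendment that must precede phase 2:

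1. Define the primary response set as all eligible patients with measurable disease at baseline who receive at least one dose of study drug.
2. Count anyone in that set without a documented CR or PR by week 16 as a non-responder, whatever the reason, including no post-baseline scan.
3. Apply the Simon counts (23/67, 20/34 and 23/56) to that set, and state that patients are not replaced.
4. Keep the rate among evaluable patients as a sensitivity analysis.
5. State that p0 and p1 are all-treated rates.

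Most of this is wording. The reported rate will be slightly less favourable. The possible real cost lies in item 5: if p1 was set with evaluable patients in mind, power must be restated for a plausible f (0.66, 0.74 and 0.72 at f = 10% for pancreas, colorectal and agnostic), and the sample sizes may need another look.
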